#### **4.4.1.3 Supportive Analyses**

If there is a difference of 10% or more in the Overall number of subjects between PP and mITT populations, a summary of the primary efficacy variable will be presented for all subjects in the PP population (Table 14.2.2.1.2), mean and SE will be presented graphically over time (Figure 14.2.2.1.4) and the same MMRM model applied to the primary analysis will be performed on the PP population (Table 14.2.2.2.2).

#### **4.4.2 Secondary Efficacy Endpoints**

All secondary endpoint analyses will be performed on the mITT population. Other than the sequential testing strategy for comparing the Overall NBS between products (see [Section 4.4](#)), there will be no adjustment for multiplicity performed for any other secondary endpoints detailed in this section.

For all the secondary efficacy variables described in subsections below, the comparisons of interest will be the 'Toothpaste/Mouthwash versus Negative Control' and 'Reference Toothpaste versus Negative Control'. Secondary efficacy variables will be analyzed using the same MMRM model described above for the primary endpoint, but with Baseline Overall NBS replaced with the Baseline of the respective endpoint:

##### **Toothpaste/Mouthwash versus Negative Control:**

- Baseline Overall NBS for Overall NBS at Week 6; Baseline Interproximal NBS for Interproximal NBS at Week 6 and Week 12.

- Baseline Mean Overall EBI for Mean Overall EBI at Week 6 and Week 12; Baseline Mean Interproximal EBI for Mean Interproximal EBI at Week 6 and Week 12.
- Baseline Mean Overall MGI for Mean Overall MGI at Week 6 and Week 12; Baseline Mean Interproximal MGI for Mean Interproximal MGI at Week 6 and Week 12.
- Baseline Mean Overall TPI for Mean Overall TPI at Week 6 and Week 12; Baseline Mean Interproximal TPI for Mean Interproximal TPI at Week 6 and Week 12.

**Reference Toothpaste versus Negative Control:**

- Baseline Overall NBS for Overall NBS at Week 6 and Week 12; Baseline Interproximal NBS for Interproximal NBS at Week 6 and Week 12.
- Baseline Mean Overall EBI for Mean Overall EBI at Week 6 and Week 12; Baseline Mean Interproximal EBI for Mean Interproximal EBI at Week 6 and Week 12.
- Baseline Mean Overall MGI for Mean Overall MGI at Week 6 and Week 12; Baseline Mean Interproximal MGI for Mean Interproximal MGI at Week 6 and Week 12.
- Baseline Mean Overall TPI for Mean Overall TPI at Week 6 and Week 12; Baseline Mean Interproximal TPI for Mean Interproximal TPI at Week 6 and Week 12.

Adjusted mean product differences will be provided, along with 95% CIs.

The assumption of residual normality and variance homogeneity in the MMRM analysis used to analyze secondary endpoints will be investigated through residual plots. If violated, data transformation or a nonparametric method (van Elteren test adjusting for gender stratification) will be used and the results will be provided to support the MMRM results.

**4.4.2.1 Number of Bleeding Sites at Week 6 and 12**

The Interproximal NBS score for each subject will be calculated as the number of evaluable Interproximal tooth sites (distal and mesial) with an EBI score of either 1 or 2.

The EBI score as described in [Table 4-1](#).

Descriptive statistics (n, mean, SD, SE, median, minimum, maximum) of Overall NBS at Week 6 will also be provided by study product for the mITT population (Table 14.2.2.1.1).

The raw mean and SE of the Overall NBS at Week 6 will also be presented graphically over time for each study product in Figure 14.2.2.1.3 for the mITT population

Similarly, the descriptive statistics (n, mean, SD, SE, median, minimum, maximum) of Interproximal NBS will be provided by study product for the mITT population (Table 14.2.3.1.1).

The raw mean and SE of the Interproximal NBS will be presented graphically over time for each study product in Figure 14.2.3.1.2 for the mITT population.

#### 4.4.2.1.1 Statistical Hypothesis, Model and Method of Analysis

The secondary hypothesis test will be the comparison between the ‘Toothpaste/Mouthwash vs. Negative Control’ and the ‘Reference Toothpaste vs. Negative Control’ in the mITT population. For comparison between ‘Toothpaste/Mouthwash and Negative Control’, the following null and alternative hypotheses will be evaluated:

- H0: There is no difference in the Overall NBS at Week 6 between the Toothpaste/Mouthwash and Negative Control.
- H1: There is a difference in the Overall NBS at Week 6 between the Toothpaste/Mouthwash and Negative Control.
- H0: There is no difference in the Interproximal NBS at Week 6 and 12 between the Toothpaste/Mouthwash and Negative Control.
- H1: There is a difference in the Interproximal NBS at Week 6 and 12 between the Toothpaste/Mouthwash and Negative Control.

For comparison between ‘Reference Toothpaste and Negative Control’, the following null and alternative hypotheses will be evaluated:

- H0: There is no difference in the Overall NBS at Week 6 and 12 between the Reference Toothpaste and Negative Control.
- H1: There is a difference in the Overall NBS at Week 6 and 12 between the Reference Toothpaste and Negative Control.
- H0: There is no difference in the Interproximal NBS at Week 6 and 12 between the Reference Toothpaste and Negative Control.
- H1: There is a difference in the Interproximal NBS at Week 6 and 12 between the Reference Toothpaste and Negative Control.

Overall and Interproximal NBS will be analyzed as described for primary analysis ([Section 4.4.1.2](#)), using the Baseline Overall/Interproximal NBS value as covariate respectively. The adjusted means and SEs of the two study products together with the product difference, SE, 95% CI of the difference and p-value will be provided in Table 14.2.2.2.1 (Overall NBS) and in Table 14.2.3.2.1 (Interproximal NBS) for the mITT population. The % adjusted mean difference will also be presented.

#### 4.4.2.2 Expanded Bleeding Index at Week 6 and 12

The EBI will be assessed at each evaluable tooth site for each subject at each visit as described in [Section 4.4.1.1](#), according to the scoring system in [Table 4-1](#).

EBI score has a range of 0 to 2.

The Mean Overall EBI score for each subject will be calculated as the average index value over all tooth sites scored as follows:

- Mean Overall EBI Score = Sum of index values over all evaluable tooth sites/ Number of evaluable tooth sites.

The Mean Interproximal EBI score for each subject will be calculated as the average index value over all Interproximal tooth sites (distal and mesial) scored as follows:

- Interproximal Mean EBI Score = Sum of index values over all evaluable Interproximal tooth sites (distal and mesial) /Number of evaluable Interproximal tooth sites (distal and mesial).

Descriptive statistics (n, mean, SD, SE, median, minimum, maximum) will be presented at each time point (Observed value and change from baseline) in Table 14.2.4.1.1 (Overall EBI) and in Table 14.2.5.1.1 (Interproximal EBI) for all subjects in the mITT population by study product.

Raw means ( $\pm$  SE) at each time point will be plotted by study product in Figure 14.2.4.1.2 (Overall EBI) and in Figure 14.2.5.1.2 (Interproximal EBI) for all subjects in the mITT population.

Individual data for the EBI Score will be listed for each subject by study product and visit in Listing 16.2.6.2.1, and individual data for the derived EBI score (Overall and Interproximal, respectively), will be listed for each randomized subject in Listing 16.2.6.2.2, by study product and visit for all randomized subjects. The % adjusted mean difference will also be presented.

#### **4.4.2.3 Statistical Hypothesis, Model, and Method of Analysis**

For comparison between ‘Toothpaste/Mouthwash and Negative Control’, the following null and alternative hypotheses will be evaluated:

- H0: There is no difference in Mean Overall EBI score at Week 6 and 12 weeks between the Toothpaste/Mouthwash and Negative Control.
- H1: There is a difference in Mean Overall EBI score at Week 6 and 12 between the Toothpaste/Mouthwash and Negative Control.
- H0: There is no difference in Mean Interproximal EBI score at Week 6 and 12 between the Toothpaste/Mouthwash and Negative Control.
- H1: There is a difference in Mean Interproximal EBI score at Week 6 and 12 between the Toothpaste/Mouthwash and Negative Control.

For comparison between ‘Reference Toothpaste and Negative Control’, the following null and alternative hypotheses will be evaluated:

- H0: There is no difference in the Mean Overall EBI at Week 6 and 12 between the Reference Toothpaste and Negative Control.
- H1: There is a difference in the Mean Overall EBI at Week 6 and 12 between the Reference Toothpaste and Negative Control.

- H0: There is no difference in the Mean Interproximal EBI at Week 6 and 12 between the Reference Toothpaste and Negative Control.
- H1: There is a difference in the Mean Interproximal EBI at Week 6 and 12 between the Reference Toothpaste and Negative Control.

Overall and Interproximal EBI will be analyzed as described for primary analysis ([Section 4.4.1.2](#)), using the Baseline Mean Overall and Interproximal EBI value respectively as covariate. The adjusted means and SEs of the two study products together with the product difference, SE, 95% CI of the difference and p-value will be provided in Table 14.2.4.2.1 (Overall EBI) and in Table 14.2.5.2.1 (Interproximal EBI) for the mITT population. The % adjusted mean difference will also be presented.

#### 4.4.2.4 Mean Modified Gingival Index at Week 6 and 12

The MGI assessment is a non-invasive evaluation which focuses on the visual symptoms of gingivitis (for example, redness, texture, edema). The MGI will be assessed on the buccal and lingual marginal gingiva and interdental papillae of all scorable teeth (second permanent molar to second permanent molar in each arch) by an appropriately qualified examiner. Three scores will be recorded buccally/labially (papilla and margin) and three scores lingually/palatally (papilla and margin). The scoring of the MGI will be performed under dental office conditions using a standard dental light for illuminating the oral cavity.

The MGI score has a range of 0 to 4.

The MGI scoring system is described in [Table 4-2](#).

**Table 4-2 Modified Gingival Index**

Score	Description
0	Absence of inflammation
1	Mild inflammation; slight change in colour, little change in colour; little change in texture of any portion of the marginal or papillary gingival unit.
2	Mild inflammation; criteria as above but involving the entire marginal or papillar gingival unit.
3	Moderate inflammation; glazing, redness, edema, and/or hypertrophy of the marginal or papillary gingival unit.
4	Severe inflammation; marked redness, edema and/or hypertrophy of the marginal or papillary gingival unit, spontaneous bleeding, congestion, or ulceration.
9	Missing tooth or not qualified tooth

The Mean Overall MGI score for each subject will be calculated as the average index value over all tooth sites scored as follows:

- Mean Overall MGI Score = Sum of Index values over all evaluable tooth sites/Number of evaluable tooth sites.

The Mean Interproximal MGI score for each subject will be calculated as the average index value over all Interproximal tooth sites (distal and mesial) scored as follows:

- Mean Interproximal MGI Score = Sum of index values over all evaluable Interproximal tooth sites (distal and mesial) /Number of evaluable Interproximal tooth sites (distal and mesial).

Descriptive statistics (n, mean, SD, SE, median, minimum, maximum) will be presented at each time point (Observed value and change from baseline) in Table 14.2.6.1.1 (Overall MGI) and in Table 14.2.7.1.1 (Interproximal MGI) for all subjects in the mITT population by study product.

The raw mean and SE of the MGI will be presented graphically over time for each study product in Figure 14.2.6.1.2 (Overall MGI) and in Figure 14.2.7.1.2 (Interproximal MGI) for the mITT population.

Individual data for the MGI will be listed for each subject by study product and visit in Listing 16.2.6.3.1 for all randomized subjects and individual data for the derived MGI score (Overall and Interproximal) will be listed for each subject in Listing 16.2.6.3.2, by study product and visit for all randomized subjects. The % adjusted mean difference will also be presented.

#### **4.4.2.5 Statistical Hypothesis, Model and Method of Analysis**

For comparison between ‘Toothpaste/Mouthwash and Negative Control’, the following null and alternative hypotheses will be evaluated:

- H0: There is no difference in Mean Overall MGI score at Week 6 and 12 between the Toothpaste/Mouthwash and Negative Control.
- H1: There is a difference in Mean Overall MGI score at Week 6 and 12 between the Toothpaste/Mouthwash and Negative Control.
- H0: There is no difference in Mean Interproximal MGI score at Week 6 and 12 between the Toothpaste/Mouthwash and Negative Control.
- H1: There is a difference in Mean Interproximal MGI score at Week 6 and 12 between the Toothpaste/Mouthwash and Negative Control.

For comparison between ‘Reference Toothpaste and Negative Control’, the following null and alternative hypotheses will be evaluated:

- H0: There is no difference in the Mean Overall MGI at Week 6 and 12 between the Reference Toothpaste and Negative Control.
- H1: There is a difference in the Mean Overall MGI at Week 6 and 12 between the Reference Toothpaste and Negative Control.

- H0: There is no difference in the Mean Interproximal MGI at Week 6 and 12 between the Reference Toothpaste and Negative Control.
- H1: There is a difference in the Mean Interproximal MGI at Week 6 and 12 between the Reference Toothpaste and Negative Control.

MGI (Overall and Interproximal) will be analyzed as described for primary analysis ([Section 4.4.1.2](#)), using the Baseline Mean Overall and Interproximal MGI value respectively as covariate. The adjusted means and SEs of the two product groups together with the product difference, SE, 95% CI of the difference and p-value will be provided in Table 14.2.6.2.1 (Overall MGI) and in Table 14.2.7.2.1 (Interproximal Mean MGI) for the mITT population. The % adjusted mean difference will also be presented.

#### 4.4.2.6 Mean Turesky Plaque Index at Week 6 and 12

TPI will be used to assess plaque on all gradable teeth meeting the inclusion/ exclusion criteria and will be performed by an appropriately qualified examiner. Only natural teeth can be assessed. This means no crowns, bridges, and teeth with fillings (surface that has 50% of the surface gradable or no more than 50% of the surface filled) which, in the examiner's judgment, would prevent an accurate grading should be assessed. Third molars should not be assessed.

The plaque will first be disclosed using a plaque disclosing dye solution, in agreement with the manufacturer's instructions. The TPI will be assessed on the facial and lingual surfaces of each scorable tooth (second molar to second molar). Three scores should be recorded buccally/ labially (distal, body, mesial sites) and three scores lingually / palatally (distal, body, mesial sites).

The TPI scoring system is described in [Table 4-3](#).

**Table 4-3 Turesky Plaque Index**

Score	Description
0	No plaque
1	Separate flecks of plaque at the cervical margin
2	Thin continuous band of plaque (up to 1 mm) at the cervical margin
3	Band of plaque wider than 1 mm but covering < 1/3 of the tooth surface
4	Plaque covering ≥ 1/3 but < 2/3 of the tooth surface
5	Plaque covering ≥ 2/3 of the tooth surface
9	Missing tooth or not qualified tooth

The Mean Overall TPI score for each subject will be calculated as the average index value over all tooth sites scored as follows:

- Mean Overall TPI Score = Sum of index values over all evaluable tooth sites/Number of evaluable tooth sites.

The Mean Interproximal TPI score for each subject will be calculated as the average index value over all Interproximal tooth sites (distal and mesial) scored as follows:

- Mean Interproximal TPI Score = Sum of index values over all evaluable Interproximal tooth sites (distal and mesial) /Number of evaluable Interproximal tooth sites (distal and mesial).

The evaluable tooth sites are those scored as 0, 1, 2, 3, 4 or 5.

The Overall TPI score and Mean Interproximal TPI score have a range of 0 to 5.

Descriptive statistics (n, mean, SD, SE, median, minimum, maximum) will be presented at each time point (Observed value and change from baseline) in Table 14.2.8.1.1 (Overall TPI) and in Table 14.2.9.1.1 (Interproximal TPI) for all subjects in the mITT population by study product.

The raw mean and SE of the TPI will be presented graphically over time for each study product in Figure 14.2.8.1.2 (Overall TPI) and in Figure 14.2.9.1.2 (Interproximal TPI) for the mITT population.

Individual data for the TPI assessment at each evaluable tooth site will be listed for each subject in Listing 16.2.6.4.1, and individual data for the derived TPI score (Overall and Interproximal, respectively), will be listed for each subject in Listing 16.2.6.4.2, by study product and visit for all randomized subjects. The % adjusted mean difference will also be presented.

#### **4.4.2.7 Statistical Hypothesis, Model and Method of Analysis**

For comparison between ‘Toothpaste/Mouthwash and Negative Control’, the following null and alternative hypotheses will be evaluated:

- H0: There is no difference in Mean Overall TPI score at Week 6 and 12 between the Toothpaste/Mouthwash and Negative Control.
- H1: There is a difference in Mean Overall TPI score at Week 6 and 12 between the Toothpaste/Mouthwash and Negative Control.
- H0: There is no difference in Mean Interproximal TPI score at Week 6 and 12 between the Toothpaste/Mouthwash and Negative Control.
- H1: There is a difference in Mean Interproximal TPI score at Week 6 and 12 between the Toothpaste/Mouthwash and Negative Control.

For comparison between ‘Reference Toothpaste and Negative Control’, the following null and alternative hypotheses will be evaluated:

- H0: There is no difference in the Mean Overall TPI at Week 6 and 12 between the Reference Toothpaste and Negative Control.
- H1: There is a difference in the Mean Overall TPI at Week 6 and 12 between the Reference Toothpaste and Negative Control.

- H0: There is no difference in the Mean Interproximal TPI at Week 6 and 12 between the Reference Toothpaste and Negative Control.
- H1: There is a difference in the Mean Interproximal TPI at Week 6 and 12 between the Reference Toothpaste and Negative Control.

TPI (Overall and Interproximal) will be analyzed as described for primary analysis ([Section 4.4.1.2](#)), using the Baseline Mean Overall and Interproximal TPI value respectively as covariate. The adjusted means and SEs of the two product groups together with the product difference, SE, 95% CI of the difference and p-value will be provided in Table 14.2.8.2.1 (Overall TPI) and in Table 14.2.9.2.1 (Interproximal TPI) for the mITT population. The % adjusted mean difference will also be presented.

### 4.4.3 Exploratory Efficacy Variables

The exploratory endpoints comparing the Toothpaste/Mouthwash versus Reference Toothpaste will be analyzed using the same MMRM model described above for the primary and secondary endpoints.

#### 4.4.3.1 Number of Bleeding Sites at Week 6 and Week 12

The key exploratory hypothesis test will be the comparison between the 'Toothpaste/Mouthwash' versus 'Reference Toothpaste' in the mITT population.

The following null and alternative hypotheses will be evaluated:

- H0: There is no difference in the Overall NBS at Week 6 and 12 between the Toothpaste/Mouthwash and Reference Toothpaste.
- H1: There is a difference in the Overall NBS at Week 6 and 12 between the Toothpaste/Mouthwash and Reference Toothpaste.
- H0: There is no difference in the Interproximal NBS at Week 6 and 12 between the Toothpaste/Mouthwash and Reference Toothpaste.
- H1: There is a difference in the Interproximal NBS at Week 6 and 12 between the Toothpaste/Mouthwash and Reference Toothpaste.

NBS (Overall and Interproximal) will be analyzed as described for primary analysis ([Section 4.4.1.2](#)), using the Baseline Interproximal/Overall NBS value as covariate respectively. The adjusted means and SEs of the two product groups together with the product difference, SE, 95% CI of the difference and p-value will be provided in Table 14.2.2.2.1 (Overall NBS) and in Table 14.2.3.2.1 (Interproximal NBS) for the mITT population. The % adjusted mean difference will also be presented.

#### 4.4.3.2 Expanded Bleeding Index at Week 6 and Week 12

For comparison between 'Toothpaste/Mouthwash and Reference Toothpaste', the following null and alternative hypotheses will be evaluated:

- 
- H0: There is no difference in the Mean Overall EBI at Week 6 and 12 between the Toothpaste/Mouthwash and Reference Toothpaste.
  - H1: There is a difference in the Mean Overall EBI at Week 6 and 12 between the Toothpaste/Mouthwash and Reference Toothpaste.
  - H0: There is no difference in the Mean Interproximal EBI at Week 6 and 12 between the Toothpaste/Mouthwash and Reference Toothpaste.
  - H1: There is a difference in the Mean Interproximal EBI at Week 6 and 12 between Toothpaste/Mouthwash and Reference Toothpaste.

EBI (Overall and Interproximal) will be analyzed as described for primary analysis ([Section 4.4.1.2](#)), using the Baseline Mean Interproximal/Overall EBI value as covariate respectively. The adjusted means and SEs of the two product groups together with the product difference, SE, 95% CI of the difference and p-value will be provided in Table 14.2.4.2.1 (Overall EBI) and in Table 14.2.5.2.1 (Interproximal EBI) for the mITT population. The % adjusted mean difference will also be presented.

#### **4.4.3.3 Mean Modified Gingival Index at Week 6 and Week 12**

For comparison between ‘Toothpaste/Mouthwash and Reference Toothpaste’, the following null and alternative hypotheses will be evaluated:

- H0: There is no difference in the Mean Overall MGI at Week 6 and 12 between the Toothpaste/Mouthwash and Reference Toothpaste.
- H1: There is a difference in the Mean Overall MGI at Week 6 and 12 between the Toothpaste/Mouthwash and Reference Toothpaste.
- H0: There is no difference in the Mean Interproximal MGI at Week 6 and 12 between the Toothpaste/Mouthwash and Reference Toothpaste.
- H1: There is a difference in the Mean Interproximal MGI at Week 6 and 12 between Toothpaste/Mouthwash and Reference Toothpaste.

MGI (Overall and Interproximal) will be analyzed as described for primary analysis ([Section 4.4.1.2](#)), using the Baseline Mean Interproximal/Overall EBI value as covariate respectively. The adjusted means and SEs of the two product groups together with the product difference, SE, 95% CI of the difference and p-value will be provided in Table 14.2.6.2.1 (Overall MGI) and in Table 14.2.7.2.1 (Interproximal MGI) for the mITT population. The % adjusted mean difference will also be presented.

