8.3.4 Other Analysis(es)

Exploratory Analysis(es)

Toothpaste/Mouthwash Compared to Reference Toothpaste

The exploratory endpoints comparing the Toothpaste/Mouthwash (a toothpaste containing 0.454% w/w SnF₂ with a mouthwash containing 0.07% w/w CPC) to the SnF₂ Toothpaste (toothpaste containing 0.454% w/w SnF₂) will be analysed using the same MMRM model described above for the primary and secondary endpoints.

Exit Satisfaction Survey Questionnaire (toothpaste/mouthwash treatment arm)

A summary of the number and percentage of subjects reporting at each level of the NRS and the cumulative number of subjects reporting at each level or higher at Week 12 will be presented, and the numeric (integer) NRS score at Week 12 will be summarized descriptively, by the test product toothpaste and the test product mouthwash.

Property of Haleon- Confidential

May not be used, divulged, published or otherwise disclosed without the consent of Haleon

CCI

Abbreviated Clinical Protocol Template v1.0

Subject free text comments will be listed after each NRS rating.

In addition to each NRS, subjects will be asked whether they would recommend the products to their family and friends who have gum problems at the end of the study. Responses (“yes” or “no”) will be summarised by the number and percentage of subjects in the test product toothpaste and the test product mouthwash treatment respectively.

Repeatability of Examiner

The repeatability of the examiner in conducting the MGI and TPI assessments will also be performed for a random sample of subjects. The repeat assessments will be compared to the original assessments. The repeat assessments will not to be used in any efficacy analysis.

The first and second assessments of each index will be analyzed with a Fleiss-Cohen weighted kappa coefficient (κ), along with the 95% CI, to assess the intra-examiner reliability. Reliability will be deemed: Excellent if $\kappa > 0.75$, Fair to good if $0.4 \leq \kappa \leq 0.75$ and Poor if $\kappa < 0.4$. This analysis will be conducted on each respective index repeatability population (MGI population and TPI population).

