#### **4.4.3.4 Mean Turesky Plaque Index at Week 6 and Week 12**

For comparison between ‘Toothpaste/Mouthwash and Reference Toothpaste’, the following null and alternative hypotheses will be evaluated:

[figure not shown]
- H0: There is no difference in the Mean Overall TPI at Week 6 and 12 between the Toothpaste/Mouthwash and Reference Toothpaste.
- H1: There is a difference in the Mean Overall TPI at Week 6 and 12 between the Toothpaste/Mouthwash and Reference Toothpaste.
- H0: There is no difference in the Mean Interproximal TPI at Week 6 and 12 between the Toothpaste/Mouthwash and Reference Toothpaste.
- H1: There is a difference in the Mean Interproximal TPI at Week 6 and 12 between Toothpaste/Mouthwash and Reference Toothpaste.

TPI (Overall and Interproximal) will be analyzed as described for primary analysis ([Section 4.4.1.2](#)), using the Baseline Mean Interproximal/Overall TPI value as covariate respectively. The adjusted means and SEs of the two product groups together with the product difference, SE, 95% CI of the difference and p-value will be provided in Table 14.2.8.2.1 (Overall TPI) and in Table 14.2.9.2.1 (Interproximal TPI) for the mITT population. The % adjusted mean difference will also be presented.

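### The exploratory toothpaste/mouthwash versus SnF2 toothpaste sections of the SAP name mismatched baseline covariates (EBI for MGI, and overall and interproximal reversed), contradicting the SAP's own rule; a minor correction before unblinding

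*SAP*

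**What the plan says.** The general rule is stated clearly. SAP 4.4.2 takes the primary model for the secondary endpoints, "but with Baseline Overall NBS replaced with the Baseline of the respective endpoint". SAP 4.4.3 opens by saying that the exploratory comparisons "will be analyzed using the same MMRM model described above for the primary and secondary endpoints", and protocol 8.3.4 says the same ("will be analysed using the same MMRM model described above for the primary and secondary endpoints"). Protocol 8.3.2 lists the pairs one by one: overall MGI with baseline overall MGI, interproximal MGI with baseline interproximal MGI, and likewise for the other indices.

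The index-specific exploratory sections then depart from that rule:

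- **4.4.3.1 (NBS):** "using the Baseline Interproximal/Overall NBS value as covariate respectively". Right index, reversed order.
- **4.4.3.2 (EBI):** right index, reversed order.
- **4.4.3.3 (MGI):** "MGI (Overall and Interproximal) will be analyzed as described for primary analysis", but "using the Baseline Mean Interproximal/Overall EBI value as covariate respectively". Wrong index, reversed order.
- **4.4.3.4 (TPI):** "using the Baseline Mean Interproximal/Overall TPI value as covariate respectively". Right index, reversed order.

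All four sections list the outcomes as overall, then interproximal. By contrast, the secondary MGI section, SAP 4.4.2.5, reads "using the Baseline Mean Overall and Interproximal MGI value respectively as covariate": right index, matching order.

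**The concern.** These clauses specify the model that a programmer will fit. Someone working from 4.4.3.3 would enter baseline EBI for MGI; someone working from the opening of 4.4.3 and the rule in 4.4.2 would enter baseline MGI. A SAP that supports both has not pre-specified either, and a choice made after unblinding would be open to criticism.

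The contrast is also of interest in its own right. The two arms use the same SnF2 toothpaste, so it is the only planned comparison that shows what adding the mouthwash contributes, and protocol 1.1 names it as something the study will explore.

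There is a reporting consequence too. The secondary and exploratory MGI results are both assigned to Tables 14.2.6.2.1 (overall) and 14.2.7.2.1 (interproximal). If the clauses were followed, one table would hold contrasts and adjusted means from models with different covariates, and the toothpaste/mouthwash adjusted mean could take two values in it.

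**Working it through.** **Text check.** In the secondary sections (SAP 4.4.2.1.1 for NBS, 4.4.2.3 for EBI, 4.4.2.5 for MGI, 4.4.2.7 for TPI) index and order both match the outcomes: 4 of 4 correct. In the exploratory sections the order is reversed in 4 of 4, and the index is wrong in 1 of 4 (MGI). The covariate clause in 4.4.3.3 is word for word that of 4.4.3.2, which suggests a paste from the EBI section. Table 5-1 lists three changes from the protocol (the recommendation question, OST recording and OHT recording), none concerning covariates.

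**Literal reading.** Overall MGI is adjusted for baseline interproximal EBI, and interproximal MGI for baseline overall EBI. For NBS, EBI and TPI the overall score is adjusted for the interproximal baseline, and the reverse.

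**Size.** The plan has no figure to reproduce: the effect size, SD and power are redacted, and no baseline to follow-up correlation is given. What follows is an illustration under assumed correlations. It treats the Week 12 contrast as an analysis of covariance with one baseline covariate, where the residual variance is proportional to 1 − r². Let r1 be the correlation of follow-up with its own baseline, and r2 the correlation with the covariate named. The SE ratio is

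R = √[(1 − r2²) / (1 − r1²)].

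Set the true difference so that the matching baseline gives 80% power at two-sided 5%. With about 60 evaluable subjects per arm that difference is (1.960 + 0.842) × √(2/60) = 0.511 SD before adjustment, and 0.511 × √(1 − r1²) after it. Power with the other covariate is then Φ(2.802/R − 1.960); the sample size cancels.

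| Case | r1 | r2 | R | Power |
|---|---|---|---|---|
| Wrong index | 0.3 | 0.1 | √(0.99/0.91) = 1.043 | 76.6% |
| Wrong index | 0.5 | 0.4 | √(0.84/0.75) = 1.058 | 75.4% |
| Wrong index | 0.5 | 0.2 | √(0.96/0.75) = 1.131 | 69.7% |
| Wrong index | 0.6 | 0.3 | √(0.91/0.64) = 1.192 | 65.2% |
| Wrong index | 0.7 | 0.3 | √(0.91/0.51) = 1.336 | 55.5% |
| Wrong index, extreme corner | 0.7 | 0.1 | √(0.99/0.51) = 1.393 | 52.0% |
| Region swap only | 0.5 | 0.45 | √(0.7975/0.75) = 1.031 | 77.5% |
| Region swap only | 0.7 | 0.63 | √(0.6031/0.51) = 1.087 | 73.1% |

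The region swap is given a small loss because the two baselines overlap heavily: interproximal sites are the distal and mesial ones, buccal and lingual, so 4 of the 6 sites on each tooth count in both scores.

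**The case against.** The strongest reply is that the governing rule is right and these clauses are a slip. The opening of SAP 4.4.3 points to the primary and secondary model, every secondary section pairs correctly, and the EBI clause looks pasted. The shared output tables, all on one template, also point to a common model, so a programmer might never fit the literal version. That stands as an account of intent. It does not remove the contradiction: the specific clauses are repeated in four sections, and each says respectively.

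The reply on importance also stands. The comparison is labelled exploratory, lies outside the sequential testing strategy and plays no part in the success criterion. The wrong index affects MGI only; the comparison that SAP 4.4.3.1 calls the key exploratory test is on NBS, where the index is right.

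A reader might infer that the mouthwash comparison would be biased. The documents do not support that. Allocation is randomized, and a mismatched pre-treatment covariate does not by itself bias the treatment difference. A reader might also infer a deliberate change of covariate; the absence of any entry in Table 5-1 and the identical wording of adjacent clauses fit a slip better.

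**Conclusion.** The SAP contradicts itself and the protocol on the baseline covariate for the exploratory comparison: in the index for MGI, and in the order of regions for all four indices. It should be corrected, but it is a minor correction to an exploratory analysis. The primary and secondary covariates are correctly stated.

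If the clauses were followed, the standard error of the MGI contrasts would be about 4% to 39% larger, and the region swap alone would add about 3% to 9%. These ranges rest wholly on assumed correlations. The 39% needs a strong own-baseline correlation (0.7) and almost none with baseline EBI (0.1), and should not be read as the expected loss.

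It might also be tempting to conclude that these contrasts must come from one three-arm model. The clauses discussed here do not establish that. SAP 4.4.1.2 names only toothpaste/mouthwash and negative control as treatment groups, and whether models are pooled or pairwise is a separate question.

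**What to change.** Before unblinding, make two edits to the SAP:

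1. In 4.4.3.3, replace EBI with MGI in the covariate clause.
2. In 4.4.3.1 to 4.4.3.4, state the pairing outright: Baseline Overall [index] for Overall [index] and Baseline Interproximal [index] for Interproximal [index]. This removes the dependence on word order.

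Four sentences change. The protocol, the data collected, the sample size and the table shells stay as they are. No entry in Table 5-1 is needed, because the corrected text agrees with protocol 8.3.2 and 8.3.4. If the sponsor did intend the covariates as now written, that would be a departure from the protocol and should be entered in Table 5-1 with a reason.
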